	Visit 1 Day -56 to Day -1	Visit 2 Baseline Day 1	Visit 3 Day 14	Visit 4 Day 28	Visit 5 Day 56	Visit 6 Day 84 EOS	Visit 7 Day 7 ⁶	Visit 8 Phone Call Day 30
				(+/-1 day)			(+4 days)	(+/-3 days)
PD Blood Sampling ²		X	X	X	X	X	X	
PK Blood Sampling ²		X	X	X	X	X	X	
Serum Pregnancy	X							
Urine Pregnancy		X	X	X	X	X	X	
Dispense Study Medication		X	X	X	X			
Administration of Morning Dose of ATI-450 in Clinic ⁷		X	X	X	X	X		
Drug Accountability			X	X	X	X		
Adverse Events ⁵	X	X	X	X	X	X	X	X
Prior and Concomitant Medications	X	X	X	X	X	X	X	X

ECG=electrocardiogram, Hep=hepatitis, PD=pharmacodynamic, TB=tuberculosis, EOS=end of study

¹A full physical examination will be performed at screening. The brief physical examination (including signs of CAPS) will be performed at visit 6 and follow-up. Body mass index will be derived in the eCRF.

²On dosing day(s), patient diary, PGA, KSS, vitals, clinical laboratory parameters, PK, and PD will be performed before the administration of study medication.

³Vital signs will be measured prior to dosing and immediately following dosing in a semi supine position after 5 minutes' rest and will include temperature, systolic and diastolic blood pressure, pulse, and respiratory rate.

⁴ A triplicate 12-lead ECG will be recorded after the subject has been resting for at least 5 minutes in a supine position.

⁵Serious adverse event reporting will start at the time of consent. Any AE that occurs between the time of consent and dosing on Day 1 will be recorded as medical history. Treatment-emergent AEs will be collected following the first dose of study medication on Day 1.

⁶Patients should not start their anti-IL-1 therapy until all safety follow-up Day 7 assessments have been completed. However, in the event of a safety concern, patients will be allowed to return early or restart their anti-IL-1 therapy early prior to completing the safety follow-up Day 7 visit at the discretion of the investigator.

⁷ The last dose of ATI-450 will be administered in clinic on Day 84. The second dose of ATI-450 is not to be administered on Day 84.

⁸ Patients will be instructed on how to complete their patient diary at the screening visit. Patients will begin completing the patient diary 7 days prior to beginning ATI-450 administration (Day 1), or immediately beginning at the screening visit if the Day 1 visit is scheduled to occur less than 7 days after screening.

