2 STUDY OBJECTIVES AND ENDPOINTS

The objectives and endpoints for this study are provided in Table 2 below.

Table 2 Study Objectives and Endpoints

Objectives		Endpoints			
Primary	To assess the safety and tolerability of ATI-450 to maintain remission in patients with CAPS previously managed with anti-IL-1 therapy	Number and percent of adverse events (AEs) and serious adverse events (SAEs); mean change from baseline in laboratory values, vital signs, and electrocardiograms (ECGs).			
Secondary	To assess the efficacy of ATI-450 to maintain remission in patients previously managed with anti-IL-1 therapy	 Proportion of participants in disease remission. Disease remission is defined as having a Physician Global Assessment (PGA) score of absent or minimal and a high sensitivity C-reactive protein (hsCRP) and serum amyloid A (SAA) value within the normal range (≤10 mg/L) or within 30 percent of the baseline value. Proportion of participants in clinical remission. Clinical remission is defined as having a PGA score of absent or minimal. Time to relapse; where relapse is defined as a two-point worsening on the PGA scale. Proportion of participants who experience a re-emergence of disease symptoms after discontinuation of ATI-450. Re-emergence is defined as an increase in daily Key Symptom Score (KSS) ≥3 for at least two consecutive days. KSS is derived from the patient-administered daily health assessment form (DHAF). Proportion of participants with a mean KSS no more than 2 points higher than baseline for at least 6 out of 8 weeks during the treatment period. Change from baseline in PGA. Change from baseline in PGA. 			

		Change from baseline in hsCRP and SAA.
Exploratory	 To assess the Pharmacodynamics (PD) of ATI-450 in patients with CAPS To assess the pharmacokinetics (PK) of ATI-450 in patients with CAPS 	 Change from baseline in serum cytokines IL-1β, IL-1α, IL-6, IL-18 and TNF-α ATI-450 concentrations at trough

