3.2 Discussion of Study Design

The study is designed to assess the safety, tolerability, efficacy, PK, and PD of ATI-450 in patients with CAPS.

Many patients with CAPS achieve complete or near complete disease remission with currently available anti-IL-1 therapies. Therefore, the study is designed to minimize patient's time off anti-IL-1 therapy due to potentially harmful long-term complications that can result from prolonged relapse of disease symptoms.

The study is open-label and there is no washout period for anti-IL-1 therapy; patients enrolled in the trial will begin treatment with study medication (Day 1) on the day of their next scheduled dose of anti-IL-1 therapy. At the end of the 12-week treatment period, ATI-450 administration will be discontinued, and patients will delay administration of anti-IL-1 therapy until 7 days (+4 days) after the last dose of ATI-450.

The 12-week treatment period was selected to allow sufficient time to explore the efficacy of ATI-450 in maintaining disease remission, and to adequately rule out the potential for prolonged disease remission caused by the last dose of anti-IL-1 therapy. Due to its long $t_{1/2}$, this is particularly relevant in instances when canakinumab is used.

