- 11. Patient has clinically significant abnormal findings other than CAPS from physical examination conducted at screening visit (Visit 1) and at baseline visit (Visit 2) that may affect the interpretation of study data or the safety of the patient's participation in the study, per the judgment of the investigator.
- 12. Patient has a clinically important history of a medical disorder that would compromise patient safety or data quality, per the judgment of the investigator.

- 13. Blood pressure (BP) levels (in supine position after at least 5 minutes rest) <90 mmHg or >140 mmHG for systolic BP or <40 mmHG or >90 mmHg for diastolic blood pressure.
- 14. Patients with history of stroke.
- 15. Significant cardiac disease that would affect interpretation of study data or the safety of the patient's participation in the study, per the judgment of the investigator, including recent myocardial infarction or unstable angina, or heart failure with New York Heart Association Class III or IV symptoms.
- 16. Patients with the following screening or pre-dose ECG findings, specifically:
 - Evidence of atrial fibrillation, atrial flutter, complete right or left bundle branch block, Wolff-Parkinson-White Syndrome, or other significant rhythm disturbance
 - Evidence of acute ischemia
 - Screening or pre-dose baseline mean QTcF >450 msec for males or >470 msec for females (use of the ECG algorithm is acceptable for this purpose)
 - Personal or family history of congenital long QT syndrome or sudden death
 - Any other finding that is considered clinically significant
- 17. A confirmed diagnosis of Covid-19 at baseline or at any time during the study.

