informed consent from the female partner to collect information about the pregnancy and its outcome. Information on the status of the pregnant partner and the fetus will be forwarded to the sponsor. Generally, the follow-up will be no longer than 6 to 8 weeks following the estimated delivery date. Any termination of the pregnancy will be reported regardless of fetal status (presence or absence of anomalies) or indication for the procedure. Abnormal pregnancy outcomes (e.g., spontaneous abortion, fetal death, stillbirth, congenital abnormalities, ectopic pregnancy) will be considered SAEs.

5.3.4 12-lead Electrocardiogram

Triplicate 12-lead ECG will be recorded after the subject has been resting for at least 5 minutes in the supine position. as outlined in Table 1 using an ECG machine that automatically calculates the heart rate and measures PR, QRS, QT, and QTc intervals. The ECG tracing should clearly identify the patient, include the date and time of the assessment and the signature and date of the person who made the interpretation; the tracing will be archived at the study site. Abnormal, clinically significant ECG results will be recorded as AEs.

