5.3.5 Vital Signs

Vital signs will be measured prior to dosing and immediately following dosing in a semi-supine position after 5 minutes' rest and will include temperature, systolic and diastolic blood pressure, pulse, and respiratory rate. Abnormal, clinically significant vital sign results will be recorded as AEs. If known, the underlying etiology for the abnormal clinically significant vital sign will be recorded as an AE rather than the vital sign itself.

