8 STATISTICS

8.1 General Procedures

Analyses will be performed using SAS® (SAS Institute, Cary, NC, US) by the sponsor or its representatives.

The statistical analysis plan (SAP) will be approved prior to any lock of the study database and unblinding of the study data. The SAP will provide a detailed description of the statistical methods and expand on the details provided in the protocol.

Descriptive statistics (number of observations, mean, standard deviation, median, minimum, and maximum) will be provided for continuous variables, and counts and percentages will be presented for categorical variables.

Baseline is defined as the last non-missing measurement before or on the date of first administration of study medication.

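### Read literally, the date-only baseline rule in Section 8.1 makes the Day 1 post-dose reading the baseline for the vital-sign part of the primary endpoint

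*Combined protocol and SAP*

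**What the plan says.** Section 8.1 gives a single baseline definition, with no exception by variable: "Baseline is defined as the last non-missing measurement before or on the date of first administration of study medication". It mentions the date of first dose but not the time.

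Section 5.3.5 says: "Vital signs will be measured prior to dosing and immediately following dosing in a semi-supine position after 5 minutes' rest". Table 1 footnote 3 says the same. The parameters are temperature, systolic and diastolic blood pressure, pulse and respiratory rate.

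Table 1 puts vital signs and the in-clinic morning dose both at Visit 2, Day 1. Section 3.2 confirms that this is the first dose: "patients enrolled in the trial will begin treatment with study medication (Day 1) on the day of their next scheduled dose of anti-IL-1 therapy".

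The primary endpoint (synopsis; Section 2, Table 2) includes mean change from baseline in vital signs and ECGs. Section 8.4.2 says only that these will be presented descriptively. It does not say which of two same-day readings is used.

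On ECGs, Section 5.3.4 says: "Triplicate 12-lead ECG will be recorded after the subject has been resting for at least 5 minutes in the supine position". Exclusion criterion 16 refers to a mean: "Screening or pre-dose baseline mean QTcF >450 msec for males or >470 msec for females". Section 8 does not say how a triplicate is reduced to one value.

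**The concern.** A baseline for a safety summary should be the last value before exposure. Here the rule includes the whole of the first-dose date, and the schedule produces a vital-sign reading on that date after the dose. A programmer who follows Section 8.1 to the letter takes the post-dose reading as the reference and treats the pre-dose reading as superseded.

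Two consequences follow for a component of the primary endpoint. The first-dose change in vital signs cannot appear in the change-from-baseline table, because the value that would show it has become the reference. And later pre-dose readings are compared with a value taken under a different condition. The study has a single arm, so no control group would carry the same offset and cancel it.

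**Working it through.** The plan has no figure to reproduce: the sample size is set by feasibility, and no variability or effect size is given for vital signs. The check applies the rule to the records that the schedule generates.

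**Step 1. Vital-sign records up to the first-dose date, in time order**

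| Record | Dated on or before the first-dose date? | Before the first dose in time? |
|---|---|---|
| Screening | yes | yes |
| Day 1, pre-dose | yes | yes |
| Day 1, immediately post-dose | yes | no |

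- Section 8.1 rule (last record by date): the Day 1 post-dose reading.
- Date-and-time rule (last record before the first dose): the Day 1 pre-dose reading.

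**Step 2. Effect on the change from baseline**

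Let P be the Day 1 pre-dose reading, Q the Day 1 post-dose reading, Y a later reading, and d the mean of Q − P over patients.

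- Day 1 post-dose change: Q − Q = 0 under the Section 8.1 rule. It is Q − P, with mean d, under the date-and-time rule.
- Later change: Y − Q = (Y − P) − (Q − P). Its mean is the mean change from the pre-dose baseline, minus d.

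The documents give no value for d. Over an assumed range, in the units of the parameter:

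| Assumed d | Shift in later mean change (−d) |
|---|---|
| −5 | +5 |
| −2 | +2 |
| 0 | 0 |
| +2 | −2 |
| +5 | −5 |

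This applies to each of the five parameters and to every patient with both Day 1 readings, up to 10.

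**Step 3. Where in the range d is likely to lie**

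Section 1.1.3 gives a median tmax of 2.0 to 4.0 hours after single oral doses. Section 1.1.2.3 reports lower arterial pressure in mini-pigs about 2 through 6 hours after 45 mg/kg, and no effects at 5 or 15 mg/kg. A reading immediately after swallowing a tablet comes before both windows, so the drug contribution to d is probably small. What remains is the ordinary difference between a first and a repeat reading, which the documents do not quantify.

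**Step 4. Whether other variables are affected**

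Table 1 footnote 2 places the diary, PGA, KSS, laboratory, PK and PD assessments before dosing. None of them has a scheduled Day 1 post-dose repeat. For these, the date rule and the date-and-time rule select the same record. Vital signs are the only assessment that the schedule explicitly repeats after the dose.

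**The case against.** The strongest reply is that the intention is clear. Visit 2 is labelled baseline, footnote 2 lists vitals among the pre-dose assessments, and Section 8.1 leaves detail to a SAP that would normally settle record selection. The analyses are descriptive, with no test or threshold, and nothing prevents both Day 1 readings from being tabulated. The reading comes too early for much drug effect. If d is only settling on a repeat reading, a post-dose baseline is the like-for-like reference for later post-dose readings, so for those the shift is not a bias.

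Most of this bears on size, and it stands. It does not repair the rule. Footnote 2 governs when assessments are done. It does not define baseline or remove the post-dose reading that footnote 3 requires. The documents reviewed contain no separate SAP text, and Section 8.1 describes the SAP as expanding on the protocol, not correcting it. Later pre-dose readings would still be set against a post-dose reference.

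A reader might go further and infer that the rule also picks the third tracing of the ECG triplicate, or admits a post-dose ECG, and that the baseline error variance is therefore three times larger (s² against s²/3, if replicates are independent). The documents do not support this:

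- The ECG row in Table 1 carries the marker for footnote 2, the pre-dose footnote, although the footnote's text leaves ECG out of its list.
- Exclusion criterion 16 speaks of a pre-dose baseline mean QTcF.
- Section 8.1 does not say whether a measurement is one tracing or the set of three. The threefold figure holds only if each tracing counts separately, which is not established.

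The triplicate question is also independent of the date wording, and a time-of-dose rule would not answer it.

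**Conclusion.** The point holds for vital signs. As written, Section 8.1 selects the Day 1 post-dose reading as baseline for a component of the primary endpoint, and nothing in the documents overrides it. The Day 1 post-dose change is then zero by construction, and later changes from pre-dose readings shift by −d. This rests on a literal reading of the rule and on both Day 1 readings being taken as scheduled.

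The size is unknown and may be close to zero. The range of −5 to +5 units is an assumption that shows the arithmetic, not an estimate. The case for changing the rule is that it is wrong as worded and cheap to correct, not that a large distortion has been shown.

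For ECGs there is only a gap in wording: the plan does not say that the triplicate is averaged for analysis.

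**What to change.** - **Section 8.1:** define baseline as the last non-missing measurement before the first administration of study medication, by date and time. Where a clock time is missing, the pre-dose or post-dose label on the reading can decide.
- **Section 8.4.2 or the SAP:** summarise the Day 1 post-dose vital signs as a post-baseline time point, and say whether later visits are summarised from pre-dose readings, post-dose readings, or each separately.
- **Minor clarification:** state that the ECG baseline is the mean of the pre-dose triplicate, in line with exclusion criterion 16, and add ECG to the text of Table 1 footnote 2, whose marker the ECG row already carries.

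The cost is a few sentences of text and one word in a footnote. No new assessments are needed, only pre-dose and post-dose labels on readings already planned.

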8.2 Analysis Populations

- The ITT population will include all patients who have been administered at least one dose of study medication.
- The PP population will include all patients who complete 12-weeks of treatment and 4-weeks of follow up and have completed assessments.

8.3 Sample Size

The sample size for this study was determined based upon feasibility constraints as opposed to a formal power computation. Up to 10 patients are planned to be enrolled.

8.4 Statistical Methods

8.4.1 Efficacy Analyses

All efficacy summaries will be conducted on both the ITT and PP populations.

- Proportion of participants in disease remission over time; where disease remission is defined as having a PGA score of minimal or better and a hsCRP and SAA value within the normal range or within 30 percent of the baseline value (ITT and PP population).
- Proportion of participants in clinical remission over time; where clinical remission is defined as having a PGA score of minimal or better (ITT and PP population).
- Time to relapse; where relapse is defined as a two-point worsening on the PGA scale in the ITT population.

- Proportion of participants who experience a daily increase in KSS \geq 3 on at least two consecutive days after discontinuation of ATI-450 over time (PP population).
- Proportion of participants who maintain a mean KSS of no more than 2 higher than baseline for at least 6 out of 8 weeks in the ITT and PP population.
- Change from baseline in PGA and KSS scores will be reported descriptively over time (ITT and PP population).
- Change from baseline in hsCRP and SAA and percent change from baseline in hsCRP and SAA will be summarized over time using continuous statistical summary measures. Determination of sustained treatment effect for hsCRP and SAA will be based upon the median percent change from baseline in the ITT and PP population.

8.4.2 Safety Analyses

The Safety population will be used for the analysis of safety data (AEs, exposure to study medication, clinical laboratory, vital signs, and ECG).

AEs will be coded with the MedDRA. TEAEs are defined as AEs with an onset date on or after the date of first administration of study medication and before the date of last administration of study medication + 30 days. TEAEs will be presented by system organ class and preferred term in frequency tables. Patients with multiple AEs will be counted only once within each preferred term and system organ class. Key patient information for patients with an AE with an outcome of death, patients with SAEs, and patients with an AE leading to discontinuation of study medication will be listed.

Laboratory data (hematology, serum chemistry, coagulation, lipids, and urinalysis) will be converted to Système International units for reporting and processing purposes. Absolute values and changes from baseline will be presented descriptively. Laboratory data outside study-specific reference ranges will be listed.

Vital signs and ECG parameters will be presented descriptively.

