1.1.3 Clinical Studies

A single and multiple dose ascending study of ATI-450 in healthy volunteers has been conducted: ATI-450-PKPD-101.

ATI-450-PKPD-101 consisted of multiple parts. A total of 32 male and female subjects were enrolled into Part A of the study where 4 ascending single doses (10 mg, 30 mg, 50 mg, and 100 mg) were explored. Eight subjects were randomized at each dose level to receive a single oral dose of ATI-450 (n=6) or placebo (n=2). The 50 mg cohort was repeated following a high fat, high calorie breakfast to explore the fed-fasting PK of ATI-450.

In Part B, 3 ascending multiple doses (10 mg BID, 30 mg BID, and 50 mg BID) were explored in 30 male and female subjects. Ten subjects were randomized to receive multiple oral doses (6.5 days) of ATI-450 (n=8) or placebo (n=2) at each dose level.

Data demonstrates that ATI-450 was well tolerated at all doses in the study. No SAEs or severe intensity events were reported. The most common AEs (reported by 2 or more subjects who received ATI-450) were dizziness, headache, upper respiratory tract infection, constipation, and abdominal pain. All events were of mild intensity. A trend of a decrease in ANC was observed concurrent with dosing of ATI-450 without correlated clinical sequelae. No subject had an ANC value <500 cells/ μ L. Other laboratory findings were generally unremarkable.

After single oral doses (10 mg to 100 mg), ATI-450 was rapidly absorbed with median time to maximum plasma concentration (t_{max}) values ranging from 2.0 to 4.0 hours. Systemic exposure to ATI-450 (as measured by mean maximum plasma concentration [C_{max}] and area under the concentration-time curve from time 0 to infinity [AUC_{0-∞}]) increased approximately proportionally with dose between 10 and 100 mg, suggesting that the PKs of ATI-450 are dose-independent (i.e., linear) over the dose range evaluated. Elimination of ATI-450 from plasma was moderately slow, with mean terminal half-life $t_{1/2}$ values ranging from approximately 9 to 11 hours. After oral administration of ATI-450 at 100 mg with a standardized high fat, high-calorie breakfast, the median t_{max} was delayed (6.0 hours versus 2.0 hours), but there did not appear to be any appreciable impact on systemic exposure to ATI 450 (C_{max} was ~14% lower and AUC_{0-∞} was ~10% higher in the fed state).

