3 STUDY PLAN

3.1 Overall Study Design and Plan

The study visit schedule and planned assessments at each visit are detailed in Table 1.

This is a Phase 2a, open-label, single-arm study to investigate the safety, tolerability, efficacy, PK, and PD of ATI-450 to maintain remission in patients with CAPS previously managed with anti-IL-1 therapy. Up to 10 patients are planned to be enrolled in the study. The study will consist of an up to 8-week screening period, a 12-week treatment period, and a 4-week safety follow-up period. The total duration of the study for patients remaining in the study until their final safety follow-up assessment will be up to 24 weeks.

The investigator will obtain signed informed consent from the patient before any study procedures are performed. For further details regarding the informed consent process, see Section 9.3. During the screening visit each patient will be required to have all assessments performed as outlined in the Schedule of Assessments (Table 1).

Patients whose eligibility is confirmed at baseline will begin dosing ATI-450 tablets (50 mg BID). Such patients will be in protocol-defined remission due to prior treatment with an anti-IL-1 biologic. Dosing will begin on the day that the next dose of their anti-IL-1 therapy is scheduled at which time anti-IL-1 therapy will be discontinued.

The first dose of ATI-450 (50 mg BID) will be taken at the following times (based on anti-IL-1 therapy):

- Anakinra: 24 hours (+/- 1 hour) after last administration or at approximate time of regular anakinra dose.
- Canakinumab: 8 weeks (+/- 1 week) after last administration.
- Rilonacept: 1 week (+/- 1 day) after last administration.

ATI-450 will be administered orally for 12-weeks. Patients will attend clinic visits on Days 14, 28, 56, and 84 (+/-1 day) for safety, efficacy, PK and PD assessments. Patients will begin recording disease symptoms in their daily diary card 7 days prior to beginning administration of ATI-450, or immediately starting at the screening visit if the Day 1 visit is scheduled to occur less than 7 days after the screening visit. Patients will continue to complete their diary until completion of the safety follow up Day 7 visit.

At the end of 12-weeks, Day 84 (+/- 1 day), patients will stop ATI-450 and conduct end of study assessments. Patients will complete safety follow-up visits on site 7 Days (+4 days) after the last dose of ATI-450 and via a phone call 30 Days (+/-3 days) after the last dose.

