Patients should not start their anti-IL-1 therapy until all safety follow-up Day 7 assessments have been completed. However, in the event of a safety concern, patients will be allowed to return

early or restart their anti-IL-1 therapy prior to completing the safety follow-up Day 7 visit at the discretion of the investigator.

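### The planned treatment-emergent AE table does not separate events on ATI-450 from those in the untreated gap or after anti-IL-1 restart

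*Combined protocol and SAP*

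**What the plan says.** Adverse events and serious adverse events, as number and percent, head the primary endpoint (section 2). Section 8.4.2, like the synopsis, opens the treatment-emergent window at the first dose and closes it "before the date of last administration of study medication + 30 days". On layout it says: "TEAEs will be presented by system organ class and preferred term in frequency tables". On counting it says: "Patients with multiple AEs will be counted only once within each preferred term and system organ class". It names no breakdown by period, by on or off drug, or by relationship. Its patient listings cover deaths, serious events and events leading to discontinuation of study medication.

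The treatment sequence inside that window is in sections 3.1 and 3.2:

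- **Stop:** "At the end of 12-weeks, Day 84 (+/- 1 day), patients will stop ATI-450 and conduct end of study assessments".
- **Gap:** "patients will delay administration of anti-IL-1 therapy until 7 days (+4 days) after the last dose of ATI-450".
- **Restart:** "Patients should not start their anti-IL-1 therapy until all safety follow-up Day 7 assessments have been completed". Earlier restart is allowed for a safety concern at the investigator's discretion. No restart date is fixed, and section 6.6 permits anti-IL-1 therapy during follow-up.

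Section 1.1.3 reports mean terminal half-lives "ranging from approximately 9 to 11 hours" for ATI-450 after single doses in healthy volunteers.

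**The concern.** Safety is the primary objective and there is no control arm, so a reader of the report will look to the treatment-emergent table for what happened on ATI-450. As planned, that table adds together events on the drug, events in a deliberate interval off therapy, and events after a different drug has resumed.

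Two features make this more than a formality. First, the protocol itself looks for disease return in the gap: re-emergence of symptoms after stopping is an endpoint (section 5.2.2.1). The Key Symptom Score items are rash, fever and chills, joint pain, eye redness and pain, and fatigue. The adverse event definition in section 7.1.1 is broad, and section 7 does not exclude CAPS symptoms. Section 5.3.2 sets aside disease-related laboratory findings unless they are worse than expected, but there is no matching rule for symptoms. Second, section 1.3 describes infection, cytopenia and hypersensitivity as theoretical risks shared with other anticytokine treatments. Such an event after restart has two candidate drugs.

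The once-per-patient rule adds to this. A term reported on drug and again during a withdrawal flare becomes a single count with no period attached.

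**Working it through.** The documents give no planned figure to reproduce: the sample size is set by feasibility and the analysis is descriptive. The check is a count of days.

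**Inputs**

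- Last dose on Day 84, plus or minus 1 (section 3.1).
- Treatment-emergent onset must fall before last dose + 30 days (section 8.4.2), so the post-dose days are +1 to +29.
- Follow-up visit 7 to 11 days after the last dose (sections 3.1 and 3.2).
- Half-life 9 to 11 hours (section 1.1.3).
- At most 10 patients (section 8.3).

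**Window for a patient who completes treatment**

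- Total: 84 + 29 = 113 days (112 or 114 with the visit tolerance).
- On ATI-450: 84/113 = 74%.
- After the last dose: 29/113 = 26%.

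**Drug-free part**

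- Five half-lives: 5 × 9 = 45 h to 5 × 11 = 55 h, or 1.9 to 2.3 days.
- Fraction left after five half-lives: (1/2)^5 = 3%.
- Post-dose days beyond that: 29 − 2 = about 27.

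**Part after anti-IL-1 restart, assuming restart at the visit**

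- Restart on day +7: 6 gap days, then days +7 to +29 = 23 days; 23/113 = 20%.
- Restart on day +11: 10 gap days, then days +11 to +29 = 19 days; 19/113 = 17%.
- Restart one day after the visit: 7 to 11 gap days, then 22 to 18 days.

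**Early stoppers.** The tail stays at 29 days while on-drug time shrinks.

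- Last dose on Day 28: 29/(28 + 29) = 29/57 = 51%.
- Last dose on Day 14: 29/(14 + 29) = 29/43 = 67%.

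**Illustration.** The documents give no event rates, so assume a constant rate over the window. A term counted in a proportion p of patients over 113 days would be counted in 1 − (1 − p)^(84/113) over the on-drug days alone. For p = 10%, 30% and 50% this gives 7.5%, 23% and 40%. If events cluster in the gap, the difference is larger; if they cluster early in treatment, it is smaller.

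**Coverage by listings.** An event that begins after the last dose cannot lead to discontinuation of study medication. A non-serious event in follow-up therefore falls outside every listing named in section 8.4.2 and appears there only as part of a pooled count.

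**The case against.** A reader might infer that events in this study cannot be attributed at all. The documents do not support that. Section 7.2.2 requires a related or not-related judgement on every event, weighing underlying disease, concomitant therapy and timing. Section 7.3 requires the time of occurrence. Section 6.6 records start and end dates of all medication to the end of follow-up. With at most 10 patients, every event can be assigned to a period from these data.

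A reader might also infer that the 30-day window is wrong, or that the table declares these events to be caused by ATI-450. Neither follows. A 30-day tail is legitimate, and a treatment-emergent table reports timing. Section 7.1.1 says that an adverse event need not be causally related.

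Other points on that side have force:

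- Section 8.1 defers detailed methods to an SAP, and no separate SAP text is among the documents supplied. A split could still be specified there.
- Three weeks after restart assumes prompt restart, which is permitted but not scheduled.
- Patients have already had at least 6 months of anti-IL-1 therapy, which the protocol calls generally well tolerated, so resumption may bring few new events.
- Gap flares are also examined through the Key Symptom Score.
- No decision rule depends on the pooled percentages.

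What remains is a reporting gap. The data that would separate the periods are collected, but section 8.4.2 does not use them for ordinary treatment-emergent events. The symptom endpoint does not replace the split: it covers only diary symptoms, and the diary ends at the Day 7 visit. Causality in an open-label study is the investigator's judgement, and onset period is a useful objective complement to it.

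**Conclusion.** The point holds as a matter of presentation. The only treatment-emergent summary described pools three treatment states. About 26% of the window for a completer lies after the last dose, and 17% to 20% lies after anti-IL-1 restart if the patient restarts at the Day 7 (+4) visit. The post-restart share is smaller if restart is later and larger if it is brought forward for a safety concern. The post-dose share rises to 51% or 67% for a last dose on Day 28 or Day 14.

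These are shares of time, not of events. How many flares or post-restart events would be recorded as adverse events is not given and cannot be derived. With 10 patients, each patient counted moves a percentage by 10 points. That is true of any table of this size, but it means a single follow-up event is visible in the primary summary. The five-half-life figure describes plasma levels in healthy volunteers and does not by itself establish when drug effects end.

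The consequence is reduced clarity in answering the primary safety question. It does not invalidate the planned table.

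**What to change.** Keep the 30-day treatment-emergent table unchanged. Add to section 8.4.2, and carry into the SAP before database lock:

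1. Treatment-emergent events by onset period, counting patients once per term within each period:
   - first dose to last dose plus a short pre-specified washout, for example 3 days;
   - from then until anti-IL-1 restart;
   - after restart.
2. A rule for assigning events when anti-IL-1 restarts inside the washout cut-off.
3. A listing of all treatment-emergent events, serious or not, showing onset period and investigator causality.

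The 3 days is an analysis cut-off only. It slightly exceeds five half-lives (1.9 to 2.3 days) and implies nothing about treatment. With it, a completer who restarts at the visit contributes 84 + 3 = 87 days to the first period, 3 to 7 to the second and 23 to 19 to the third, which sums to 113.

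The cost is one table and one listing from data already recorded, with no change to visits or procedures. The downsides should be stated in the report. Cells will be small, especially in the short middle period. The cut-off is somewhat arbitrary and could move a delayed ATI-450 event out of the first period. The first period also begins without an anti-IL-1 washout, so it carries over earlier therapy, notably canakinumab, whose long half-life section 3.2 acknowledges.
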